## 5. STATISTICAL CONSIDERATIONS

### 5.1 Hypothesis for the PFS

The primary efficacy analysis will be the comparison of the distribution of PFS between the two treatment groups using a stratified logrank test at two-sided 10 % level of significance, i.e.:

$$H_0: S_t(t) = S_c(t) \text{ vs } H_1: S_t(t) \neq S_c(t), t \geq 0$$

where  $S_c(t)$  is the survival distribution function of PFS in the control arm and  $S_t(t)$  is the survival distribution function of PFS in the experimental arm.

### 5.2 Sample Size

The following assumptions are made:

- Subjects in the control arm will have a median PFS of 9 months
- Subjects in the experimental arm will have median PFS of 14 months (PFS hazard ratio of 0.64)
- Expected accrual duration will be 18 months, which leads to about 42 months of expected entire study duration
- The  $\alpha$  type I error rate is set to 10% (2-sided)
- The  $\beta$  type II error rate is set to 20% (i.e. the power of the trial will be 80%)

Under these assumptions, 150 subjects (75 per arm) will be enrolled in the trial.

### **5.3 Timing of Analyses**

The following analyses are planned:

A first analysis of safety will be performed on the first 20 subjects who complete 28 days of treatment. The steering committee will review this formal analysis.

Interim safety analyses will, then, be performed once a year until the final analysis.

The final analysis will be performed when 127 PFS events are observed in the ITT population. The trial will stop once the last subject reaches end of study treatment visit (30 days post last drug intake) and all events required for the final analysis have been observed and collected.

## **6. DEFINITIONS**

### **Baseline**

The last available assessment before or at the date of start of study treatment is taken as ‘baseline’ assessment. If subjects have no value as defined above, the baseline results will be missing.

### **Complete Response**

The radiological assessment Complete Response is defined using the RECIST v1.1 criteria.

### **Date of First Dose**

The date of first dose of study drug is derived as the first date when a nonzero dose of study drug is administered and recorded on the dose administration record of the eCRF. For the sake of simplicity, the date of first dose of study drug is also referred to as the start of the study drug.

### **Date of Last Dose**

The date of last dose of study drug is derived as the last date when a nonzero dose of study drug is administered and recorded on the dose administration record of the eCRF.

### **Last Contact Date**

The last contact date will be derived for subjects not known to have died at the analysis cut-off using the latest complete date among the following dates which precede the cut-off date:

- All assessment dates (e.g. vital signs assessment, performance status assessment, tumor assessments, etc.)
- Medication dates including concomitant medications (start or stop)
- Adverse events dates (start or stop)
- Date of last study drug administration
- Randomization date

### **Partial Response (PR)**

The radiological assessment Partial Response is defined using the RECIST v1.1 criteria.

### **Progressive Disease (PD)**

The radiological assessment Progressive Disease is defined using the RECIST v1.1 criteria.

### **RECIST**

The response to treatment will be determined according to guidelines established by the Response Evaluation Criteria In Solid Tumors (RECIST v1.1) criteria (or guidelines).

### **Stable Disease (SD)**

The radiological assessment Stable Disease is defined using the RECIST v1.1 criteria.

## Screening Phase

The screening phase is the time between the date the subject signs the informed consent and the date of randomization.

## 7. STUDY POPULATION

**The Intent-to-treat (ITT) population** will consist of all subjects who were randomized to study treatment, regardless of whether they actually received study medication. All efficacy analyses will be evaluated based on data from this population according to the treatment group they were assigned to at randomization and based on the strata they were originally assigned to at the time of randomization.

**The Safety population** will be used to assess clinical safety and tolerability and will consist of all subjects who were randomized and received at least one dose of study medication. This population will be based on the actual treatment received, if this differs from that to which the subject was randomized and will be used for the analysis of safety data.

## 8. INTERIM ANALYSIS AND EARLY STOPPING RULE

### Steering Committee

The Steering Committee (SC) will be composed of the study Co-Chairs, medical, operational and statistical representatives of TRIO and a non-voting representative from the manufacturer.

The SC will have sole responsibility for the scientific conduct and integrity of the trial. Responsibilities include review and approval of the protocol document, review and approval of protocol amendments, monitoring of accrual, compliance and safety during the conduct of the trial.

## **9. DATA SCREENING AND ACCEPTANCE**

### **9.1 General Principles**

Data Management (DM) for this study is the responsibility of TRIO.

For the planned analyses, data acceptance will be based on the creation and review of the blinded tables, listings, and figures (TLFs). In general, TLF programs will be created prior to a database snapshot or database lock. Extracts of the clinical study data will be made prior to a snapshot or lock of the database and the TLF programs will be run with the outputs reviewed for extreme, unusual, and missing values. These will be identified to Data Management and Project Management for further investigation and potential resolution prior to a snapshot or lock of the database. As issues are detected with the data entered in the database, procedures will be reviewed and programmed if necessary to ensure resolution in subsequent data transfers.

For the final analysis, all procedures will be run to ensure previously identified data issues have been resolved. The TLF programs will be run and the outputs reviewed to ensure additional data issues have not evolved. Additionally, the following items will be specifically identified for further investigation and resolution by DM prior to acceptance of the data by Biostatistics:

- Post-baseline missing disease response by radiological tumor assessment
- Outlier lab data
- Missing baseline data (e.g., labs, vitals, etc.)

The clinical study team will identify the criteria for important protocol deviation criteria. Protocol deviations that may impact the analysis and/or the interpretation of the study results include, but are not limited to:

- No disease assessments
- Inclusion/exclusion criteria not met

- Treatment administration that is not consistent with the protocol (based on the randomized treatment for each subject)

## **9.2 Data Handling and Electronic Data Transfer**

All clinical data will be entered directly by the sites users into the TRIO OCRDC database and will be transmitted electronically in the form of raw SAS® datasets. Once the final data queries have been generated and resolved, the database will be deemed “locked” and final data analysis files will be generated.

DM will provide all data to Biostatistics as raw SAS® data sets on a regular basis. Official data snapshots will be extracted from the clinical database for the final and updated analyses. The data used for all the analyses will be archived.

## **9.3 Handling of Incomplete and Missing Data**

Missing and incomplete data will be identified through a review of the tables and listings created within Biostatistics. Missing and incomplete data will be identified for investigation, and possible resolution, by DM and Project Management prior to database lock (or an official database snapshot).

**Missing Data:** All analyses and descriptive summaries will be based on the observed data. Unless otherwise specified, missing data will not be imputed or “carried forward.”

**Partial or Missing Date for Adverse Events and Concomitant Medications:**

Imputation Rules for Partial or Missing Stop Dates:

If the month and year are present, impute the last day of that month.

If only the year is present, impute December 31 of that year.

If the stop date is entirely missing, assume the event or medication is ongoing.

If a partial or complete stop date is present and the ‘ongoing’ box is checked, then it will be assumed that the adverse event or concomitant medication stopped and the stop date will be imputed if partial.

Imputation Rules for Partial or Missing Start Dates

Start Date		Stop Date						Missing
		Complete: yyyymmdd		Partial: yyyymm		Partial: yyyy		
		< 1 st dose	≥ 1 st dose	< 1 st dose yyyymm	≥ 1 st dose yyyymm	< 1 st dose yyyy	≥ 1 st dose yyyy	
Partial: yyyymm	= 1 st dose yyyymm	2	1	2	1	n/a	1	1
	≠ 1 st dose yyyymm		2		2	2	2	2
Partial: yyyy	= 1 st dose yyyy	3	1	3	1	n/a	1	1
	≠ 1 st dose yyyy		3		3	3	3	3
Missing		4	1	4	1	4	1	1

- 1 = Impute the date of first dose
- 2 = Impute the first of the month
- 3 = Impute January 1 of the year
- 4 = Impute January 1 of the stop year

## **9.4 Outliers**

Outliers will be identified through a review of TLFs. Procedures will be created to specifically look for outlier data within the laboratory and vital sign parameters.

For laboratory parameters, vital signs and clinical parameters, extreme values will be identified for investigation by Data Management and Project Management, as described in the Procedure User Requirement Specifications (URS).

Additional procedures may be created to assess potential outlier data for other parameters.

All confirmed outlier data will be included in the analyses presented in this statistical analysis plan.

## **9.5 Testing Validation Plan**

SAS® version 9.1 or higher on the Windows system will be used for all TLFs creation. The verification of the outputs, the analysis datasets as well as the review of all programs and macros created specifically for this study, will be conducted as outlined in TRIO Standard Operating Procedures and Standard Guidelines.

# **10. STATISTICAL METHODS OF ANALYSIS**

Categorical variables will be summarized in frequency tables, with the counts and percentage of subjects in each category. Percentages given in the summary tables will be rounded and thus may not always add up to exactly 100 percent. For continuous variables, summary statistics will include N, mean, standard deviation, Q1, median, Q3, minimum and maximum values (range).

SAS® version 9.1 or higher will be used for the statistical analyses.

## 10.1 Disposition of Subjects

The disposition of subjects will be tabulated using the ITT population. Number (percent) of subjects who were in each analysis population (e.g. the ITT and Safety populations), discontinued, and ongoing as of data cut-off date will be summarized by treatment group. The reason for discontinuation (both from treatment and from study participation) will be summarized considering the categories specified in the eCRF pages. Listings of disposition information and analysis population will be provided as well.

Violations of the inclusion/exclusion criteria, as well as other important protocol violations will be summarized and listed for the ITT population, by treatment arm.

The stratifications factors Bone only disease (Yes vs. No) and Prior neo/adjuvant hormonal therapy (Yes vs. No) will also be described by treatment group.

## 10.2 Demographic and Disease Characteristics

The following demographic and baseline characteristics will be summarized and listed for the ITT population by treatment group:

### Demographics:

Age,  $INT$  ( $Date\ of\ randomization - Date\ of\ birth$ ) / 365.25)

*INT = integer part*

*Due to the fact, only the year of birth is collected (YYYY), we assume the full date to be 31-Dec-YYYY*

Menopausal Status

Weight at Baseline

ECOG Status at Baseline

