4.1 Inclusion Criteria

Patients had to meet all of the following inclusion criteria to be eligible for enrollment into the trial:

1. Signed and dated informed consent document indicating that the patient (or legally acceptable representative) has been informed of all the pertinent aspects of the trial prior to enrollment.
2. Postmenopausal female, 18 years of age or older.
Postmenopausal status defined as:
 - Prior bilateral surgical oophorectomy or
 - Amenorrhea and age \geq 60 years or
 - Age < 60 years and amenorrhea for 12 or more months and FSH and estradiol in the postmenopausal ranges
3. Histologically or cytologically proven diagnosis of adenocarcinoma of the breast with evidence of locally recurrent disease not amenable to resection or radiation therapy with curative intent, or metastatic disease.
4. **HER2 negative breast cancer.** Local testing should demonstrate that the tumor is 0 or 1+ by immunohistochemistry (IHC) or is considered to be HER2 negative for gene amplification by fluorescence in-situ hybridization (FISH), chromogenic in-situ hybridization (CISH) or other in-situ hybridization (ISH) method. Central testing (required for all patients) must demonstrate that the tumor is HER2 negative by FISH or IHC.
5. **ER positive breast cancer.** Local testing should demonstrate that the tumor is ER positive. Central testing (required for all patients) must demonstrate that the tumor is ER+ with low expression (H-score[1-159]).
6. Paraffin-embedded tumor block(s) available for centralized assessment of ER, PR, and HER2. If no tumor block is available, 15 to 20 unstained slides of paraffin-embedded tissue from the tumor obtained at the initial diagnosis or prior biopsy or surgery (archived tumor tissue) will be accepted. Slides must be positively charged, frosted-end. Tumor biopsies may be from either the primary or metastatic site of disease.

When tumor tissue from the primary tumor and from metastatic sites is available, the sample from the most recent biopsy/surgery/procedure will be sent to Central laboratory.
7. Measurable disease according to RECIST 1.1 (E.A. Eisenhauer 2009) or bone-only non measurable disease according to RECIST 1.1. Previously irradiated lesions are deemed measurable only if progression is documented at the site after completion of radiation.
8. Eastern Cooperative Oncology Group (ECOG) Performance status 0 or 1 (APPENDIX 1).
9. Adequate organ function as defined by the following criteria:

- Hemoglobin ≥ 9 g/dL

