6.1.2 Registration/ Randomization

The treatment assigned was based on a dynamic minimization procedure using metastatic involvement (bone only YES or NO) and prior exposure to aromatase inhibitor (prior hormonal therapy YES or NO) as factors in the minimization algorithm. The ratio used was 1:1 and the randomization technique was using a stochastic treatment allocation algorithm based on the variance method.

The following steps for registering and randomizing a patient were chronologically performed:

The patient had to provide written informed consent prior to performing any trial specific procedure not considered standard practice by the institution.

The site registered the patient in the IWRS system (Date of ICF signed and patient year of birth needed). The system uniquely attributed a registration number to each patient in the trial. Each center was uniquely identified by a number assigned by TRIO to the investigative site. The site received a registration confirmation, containing patient registration number as well as HER2/Hormonal receptors screening form specific for the patient.

The site prepared a tumor sample fixated in formalin and embedded in paraffin (or 15 to 20 unstained slides) and shipped this sample along with the duly completed HER2/Hormonal receptors screening form to [name] laboratory (see contact details on Information Resources page - Central laboratory's address and contact details are pre-printed on the form). The tumor material can be returned to the site after testing upon site's request.

[name] laboratory entered in the IWRS system the HER2/Hormonal receptors results in a timely manner after receipt of the tumor material (usual turn-around-time was within 5 working days after receipt of the tumor material).

If (HER2-positive and/or H score not [1-159]) => The patient were moved to the Screen failure category.

If (HER2-negative and H-score [1-159]) => Screening of the patient continued at the site.

Upon completion of screening procedures and entry of screening data in TRIO eDC system, the investigator or his/her delegate checked if the patient met all eligibility criteria:

Patients who did not meet the eligibility criteria were moved to a screen failure category in the IWRS.

Patients who met all eligibility criteria were randomized in the IWRS using the following stratification factors:

Bone only disease : Yes versus No

Prior neo/adjuvant hormonal therapy : Yes versus No

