### **3. STUDY DESIGN**

This phase II, multicenter, multinational, open-label, parallel group, randomized study will compare a two-drug regimen of letrozole plus afatinib (BIBW2292) to letrozole alone in the first line treatment of ER+, HER2 negative postmenopausal Advanced Breast Cancer women with low ER expression.

Randomization is stratified by Bone only disease (Yes vs. No) and by Prior neo/adjuvant hormonal therapy (Yes vs. No). Eligible subjects will be randomly assigned in a 1:1 ratio to either:

**Arm A: Continuous regimen of oral letrozole 2.5 mg daily** until progression of disease or any other study treatment discontinuation criteria.

OR

**Arm B: Continuous regimen of oral letrozole 2.5 mg daily plus oral afatinib 30 mg daily** until progression of disease or any other study treatment discontinuation criteria.

Once the subject is discontinued from study treatment and has undergone the End of Treatment visit, the subject will enter into the follow-up phase.

This study also includes an optional exploratory research component. This optional portion is a molecular profiling assay aimed to assess the relationship of antitumor activity with the expression of selected cell cycle-related proteins and other markers that may be identified in the future. Subjects may participate in this study even if they choose not to participate in the sample banking component.

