## 11. LIST OF PLANNED TABLES, FIGURES, LISTINGS

### 11.1 Planned Tables

Title	Population	Description
Subject Disposition	ITT	Tabulates the disposition of all subjects, including the number of subjects randomized, the number of subjects that received investigational product and the number of subjects that were randomized and never received investigational product. The reason for drug discontinuation will also be summarized.  The reason for study discontinuation will be summarized.
Stratification Factors	ITT	Tabulates the stratification factors Bone only disease (Yes vs. No) and Prior neo/adjuvant hormonal therapy (Yes vs. No).
Protocol Deviations	ITT	Tabulates the protocol and the eligibility deviations.
Baseline Demographics	ITT	Tabulates summary statistics of the demographics (Age, Menopausal Status, Weight and ECOG Status at Baseline).
Disease Characteristics	ITT	Tabulates the Time from Initial Diagnosis to Randomization, the Primary Tumor Side, the Histopathological Type at Initial Diagnosis, the Histological Grade at Initial Diagnosis, the Stage IV Disease at Initial Diagnosis and the Disease

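### Setting every birth date to 31 December makes derived age correct or one year too young, never too old, so reported mean age runs about 0.4 to 0.6 year low

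*SAP*

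**What the plan says.** SAP section 10.2 defines age as the whole-number part ("INT = integer part") of the days from birth to randomisation divided by 365.25. It adds that "only the year of birth is collected (YYYY), we assume the full date to be 31-Dec-YYYY". Protocol section 6.1.2 agrees that the full birth date is not taken: the registration step lists "Date of ICF signed and patient year of birth needed". Neither document gives a reason for choosing the last day of the year, a correction or a caveat.

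The derived age goes into the baseline table for the ITT population. SAP section 11.1 describes that table thus: "Tabulates summary statistics of the demographics (Age, Menopausal Status, Weight and ECOG Status at Baseline". SAP section 10.2 and Protocol section 8.2 both call for demographics to be summarised and listed by treatment group. That output survives the early closure of enrolment, although Protocol section 2.1.2 drops the comparison between arms.

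**The concern.** When only the birth year is known, some date has to be assumed. The date chosen here lies at one end of the possible range. Every patient is treated as not yet having had her birthday in the year of randomisation, unless she is randomised on about 31 December. All errors therefore go the same way and do not average out as patients are added.

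What is at stake is the accuracy of the reported age distribution. The current protocol makes the report descriptive only, so the baseline description is one of its main products. A central date would use the same data without a systematic shift.

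**Working it through.** **Inputs from the documents**
- Assumed birth date: 31 December of the birth year (SAP 10.2).
- Formula: INT((randomisation date - birth date) / 365.25) (SAP 10.2).
- Planned accrual: "Expected accrual duration will be 18 months" (SAP 5.2).

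**Assumptions, not in the documents:** birthdays uniform over the year, and randomisation dates uniform within the stated window. The documents state no age figure, so there is nothing to reproduce first.

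**Step 1: the direction of the error.** Let D = randomisation year - birth year. Counted from 31 December of the birth year, any randomisation date before 31 December is at least D - 1 but less than D years later, so the formula returns D - 1. True age is D - 1 before the birthday and D from the birthday on. The error is therefore 0 or -1. On 31 December itself the formula can return D, which is then correct for everyone. It never exceeds true age.

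**Step 2: the size of the error.** For a patient randomised when a fraction u of the year has passed, the chance that her birthday has passed is u. The share one year too young is the average of u over the randomisation dates. Each error is exactly -1, so the mean bias is minus that average.

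| Randomisation dates | Average of u | Simulated share too young | Mean bias (years) |
|---|---|---|---|
| Uniform over whole years | 0.50 | 50.2% | -0.50 |
| 18 months from 1 January | (12 × 0.50 + 6 × 0.25) / 18 = 0.417 | 41.9% | -0.42 |
| 18 months from 1 April | (9 × 0.625 + 9 × 0.375) / 18 = 0.50 | 49.8% | -0.50 |
| 18 months from 1 July | (6 × 0.75 + 12 × 0.50) / 18 = 0.583 | 58.3% | -0.58 |
| 18 months from 1 October | (3 × 0.875 + 12 × 0.50 + 3 × 0.125) / 18 = 0.50 | 49.8% | -0.50 |

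The simulation used 200,000 patients for the first row and 60,000 for each of the others. The limits are far apart: about 5% too young if all patients were randomised in January, and 94% if all in December.

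The bias is measured against age in completed years. Against exact decimal age the mean difference in the uniform case is -1.0 year, of which -0.5 is the ordinary truncation carried by any age in completed years.

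**Step 3: the same check for 1 July.**
- Too young: u below 1/2 and birthday already passed. The integral of u from 0 to 1/2 is 1/8 = 12.5%.
- Too old: u at or above 1/2 and birthday still to come. The integral of (1 - u) from 1/2 to 1 is 1/8 = 12.5%.
- Total wrong 25%, mean bias 0. The simulation gave 12.4% too young, 12.5% too old and a bias of +0.001.

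The bias is not exactly 0 in every window. For 18 months from 1 January, (12 × 0.125 + 6 × 0.25) / 18 = 16.7% are too young and (12 × 0.125) / 18 = 8.3% too old, a bias of -0.08. Starting on 1 July mirrors this, at +0.08. Starting on 1 April or 1 October, the bias is 0 by symmetry. The share wrong is then (3/32 + 1/8 + 1/8 + 3/32) / 1.5 = 29% or (1/32 + 1/4 + 1/32) / 1.5 = 21%.

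Using 1 January instead would only reverse the present problem: about 50% too old and a bias of +0.50.

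**The case against.** The strongest reply is that no rule recovers true age from a birth year, that the SAP states its convention openly, and that the result can be read as a lower bound on completed years. The present rule never overstates age, whereas 1 July would make about 12.5% of patients one year too old. The consequence is also small. Age is not a stratification factor ("Randomization is stratified by Bone only disease (Yes vs. No) and by Prior neo/adjuvant hormonal therapy (Yes vs. No"), and any shift should be much the same in both arms. All of this stands, and it limits the weight of the point. It does not justify an end-of-range date where a central one needs no further data, because neither document says that a lower bound is intended.

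A reader might infer a more serious harm from the menopausal criterion in Protocol section 4.1. For patients without oophorectomy, amenorrhoea suffices from age 60, while below 60 the requirement is "Age < 60 years and amenorrhea for 12 or more months and FSH and estradiol in the postmenopausal ranges". A patient truly aged 60 but derived as 59 could then look like an eligibility deviation. The documents do not support this. Under Protocol section 6.1.2 the investigator or a delegate checks eligibility before randomisation. Menopausal status is a separate baseline item in the SAP. SAP section 9.1 leaves the deviation criteria to the study team and does not mention derived age. If derived age were used at that threshold, a mid-year date would also misplace some patients, including some aged 59 who would be shown as 60.

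**Conclusion.** The rule biases reported age downward, and the point is minor. Derived age is either correct or one year too young. With uniform birthdays and 18-month randomisation windows starting at different times of year, about 42% to 58% of patients are affected and mean age is biased by about -0.42 to -0.58 year. The tempting summary of exactly half the patients and exactly half a year is one case within that range. It needs randomisation dates balanced over the calendar, and the documents do not give the dates. The 18 months is also the planned accrual period, not the observed one. The direction of the error depends on none of these assumptions.

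The effect stays within the descriptive age summary and listing. SAP section 10.5.1 allows exploratory Cox models with further prognostic covariates but does not name age among them. The PFS comparison described in the SAP, the analysis populations and the eligibility rules are unaffected.

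**What to change.** In SAP section 10.2, replace 31-Dec-YYYY with a mid-year date such as 01-Jul-YYYY. Add a footnote to the demographics table saying that only birth year was collected, which date was assumed, and that individual ages may be one year out in either direction.

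The cost is one edit to the SAP and one line of code. The small downside is that some ages, about 12.5% under uniform dates, become one year too high. If the outputs have already been produced, a footnote stating the 31 December convention and its downward bias of roughly half a year would be enough.
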